#### **10.1.6 Reporting of study treatment errors including misuse/abuse**

Medication errors are unintentional errors in the prescribing, dispensing, administration or monitoring of a medicine while under the control of a healthcare professional, subject or consumer (EMA definition).

Misuse refers to situations where the medicinal product is intentionally and inappropriately used not in accordance with the protocol.

Abuse corresponds to the persistent or sporadic, intentional excessive use of a medicinal product, which is accompanied by harmful physical or psychological effects.

Study treatment errors and uses outside of what is foreseen in the protocol will be recorded on the appropriate CRF irrespective of whether or not associated with an AE/SAE and reported to Safety only if associated with an SAE. Misuse or abuse will be collected and reported in the safety database irrespective of it being associated with an AE/SAE within 24 hours of investigator's awareness.

**Table 10-2      Guidance for capturing the study treatment errors including misuse/abuse**

Treatment error type	Document in Dosing CRF (Yes/No)	Document in AE eCRF	Complete SAE form
Unintentional study treatment error	Yes	Only if associated with an AE	Only if associated with an SAE
Misuse/Abuse	Yes	Yes	Yes, even if not associated with a SAE

For more information on AE and SAE definition and reporting requirements, please see the respective sections.

## **10.2      Additional safety monitoring**

### **10.2.1    Steering committee**

The steering committee will be established and comprised of SCD and priapism medical experts as well as Novartis representatives from the Clinical Trial Team.

The steering committee will ensure transparent management of the study according to the protocol through recommending and approving modifications as circumstances require. The SC will review protocol amendments as appropriate. Together with the clinical trial team, the SC will also develop recommendations for publications of study results including authorship rules. The details of the role of the steering committee will be defined in the steering committee charter.

## **11      Data Collection and Database Management**

### **11.1    Data collection**

Designated investigator staff will enter the data required by the protocol into the Electronic Case Report Forms (eCRF). The eCRFs have been built using fully validated secure web -enabled software that conforms to 21 CFR Part 11 requirements, investigator site staff will not be given access to the EDC system until they have been trained. Automatic validation programs check for data discrepancies in the eCRFs, allow modification and/or verification of the entered data by the investigator staff.

The investigator/designee is responsible for assuring that the data (recorded on CRFs) (entered into eCRF) is complete, accurate, and that entry and updates are performed in a timely manner. The investigator must certify that the data entered is complete and accurate.

After final database lock, the investigator will receive copies of the subject data for archiving at the investigational site.

All data should be recorded, handled and stored in a way that allows its accurate reporting, interpretation and verification.

## **11.2 Database management and quality control**

Novartis personnel (or designated CRO) will review the data entered by investigational staff for completeness and accuracy. Electronic data queries stating the nature of the problem and requesting clarification will be created for discrepancies and missing values and sent to the investigational site via the EDC system. Designated investigator site staff are required to respond promptly to queries and to make any necessary changes to the data.

Concomitant treatments and prior medications entered into the database will be coded using the WHO Drug Reference List, which employs the Anatomical Therapeutic Chemical classification system. Medical history/current medical conditions and AEs will be coded using the Medical dictionary for regulatory activities (MedDRA) terminology.

At the conclusion of a non-IRT study, the occurrence of any emergency code breaks will be determined after return of all code break reports and unused supplies to Novartis.

Once all the necessary actions have been completed and the database has been declared to be complete and accurate, it will be locked and made available for data analysis/moved to restricted area to be accessed by independent programmer and statistician. Any changes to the database after that time can only be made after a written agreement by Novartis development management.

## **11.3 Site monitoring**

Before study initiation, at a site initiation visit or at an investigator's meeting, a Novartis representative will review the protocol and data capture requirements (i.e. eSource DDE or eCRFs) with the investigators and their staff. During the study, Novartis employs several methods of ensuring protocol and GCP compliance and the quality/integrity of the sites' data. The field monitor will visit the site to check the completeness of subject records, the accuracy of data capture / data entry, the adherence to the protocol and to Good Clinical Practice, the progress of enrollment, and to ensure that study treatment is being stored, dispensed, and accounted for according to specifications. Key study personnel must be available to assist the field monitor during these visits. Continuous remote monitoring of each site's data may be performed by a centralized Novartis-affiliated Clinical Research Associate (CRA) organization. Additionally, a central analytics organization may analyze data & identify risks & trends for site operational parameters and provide reports to Novartis/sponsor clinical teams to assist with trial oversight.

The investigator must maintain source documents for each subject in the study, consisting of case and visit notes (hospital or clinic medical records) containing demographic and medical information, laboratory data, ECGs, and the results of any other tests or assessments. All information on CRFs must be traceable to these source documents in the subject's file. The investigator must also keep the original informed consent form signed by the subject (a signed copy is given to the subject).

The investigator must give the monitor access to all relevant source documents to confirm their consistency with the data capture and/or data entry. Novartis monitoring standards require full verification for the presence of informed consent, adherence to the inclusion/exclusion criteria, documentation of SAEs, and of data that will be used for all primary variables. Additional checks of the consistency of the source data with the CRFs are performed according to the

study-specific monitoring plan. No information in source documents about the identity of the subjects will be disclosed.

## **12 Data analysis and statistical methods**

Summary statistics for continuous variables will generally include the number of subjects, mean, standard deviation (SD), lower quartile (Q1), median, upper quartile (Q3), minimum, and maximum. For categorical or binary variables, the number and percent of subjects in each category will be presented.

The primary analysis of study data for the primary clinical study report (CSR) will be based on all subject data up to the Week 26 (up to assessments taken on Week 27 Day 1 before infusion). The additional data for any subjects continuing to receive study drug after this time, as allowed by the protocol, will be further summarized in a final study report once these subjects have completed or discontinued the study.

Baseline period is defined as the 12 weeks screening period prior to the first infusion of crizanlizumab 5 mg/kg at Week 1 Day 1.

### **12.1 Analysis sets**

Full Analysis Set (FAS): The FAS include all enrolled subjects to whom the study treatment has been assigned regardless of whether or not they have received at least 1 dose of study treatment or have at least 1 post-baseline assessment.

Safety Analysis Set (SAF): The SAF will consist of all subjects who received at least 1 dose of study treatment.

All efficacy analyses will be performed on subjects in FAS who have completed treatment.

### **12.2 Subject demographics and other baseline characteristics**

Demographic and other baseline disease characteristics will be listed and summarized descriptively for all subjects in the FAS as well as for those subjects in FAS who have completed the treatment.

Categorical data will be presented as frequencies and percentages. For continuous data, mean, standard deviation (SD), lower quartile (Q1), median, upper quartile (Q3), minimum and maximum will be presented.

Relevant medical histories and current medical conditions at baseline will be summarized separately, by system organ class and preferred term.

Prior disease information will also be summarized.

### **12.3 Treatments**

The Safety set will be used for the analyses below. Categorical data will be summarized as frequencies and percentages. For continuous data, mean, standard deviation (SD), lower quartile (Q1), median, upper quartile (Q3), minimum and maximum will be presented.

The duration of exposure in weeks to study drug as well as the dose intensity (computed as the ratio of actual cumulative dose received and actual duration of exposure) and the relative dose intensity (computed as the ratio of dose intensity and planned dose intensity) will be summarized by means of descriptive statistics using the Safety set.

The number of subjects with dose interruption or permanent discontinuation and the reasons will be summarized for all subjects and all dosing data will be listed.

Concomitant medications and significant non-drug therapies prior to and after the start of the study treatment will be listed and summarized according to the Anatomical Therapeutic Chemical (ATC) classification system for all subjects.

## **12.4 Analysis of the primary endpoint**

The primary objective of this study is to evaluate clinical efficacy of crizanlizumab 5 mg/kg, over 26 weeks compared to baseline in sickle cell subjects with a history of priapism.

### **12.4.1 Definition of primary endpoint**

The primary endpoint of the study is percent reduction from baseline in priapism events by 26 weeks (i.e. up to pre-infusion Week 27, Day 1). Priapism event is defined as unwanted, or painful erection lasting at least 60 minutes, self-reported.

### **12.4.2 Statistical model, hypothesis, and method of analysis**

It is expected that crizanlizumab treatment reduces priapic events by at least 25% in SCD subjects with priapism. Demonstration of significant percent reduction from baseline in priapic events will be evaluated using the following hypothesis:

$H_0: p < 0.25$ , where  $p$  is the percent reduction in priapic events by 26 weeks.

$H_1: p \geq 0.25$ , where  $p$  is the percent reduction in priapic events by 26 weeks.

If the above null hypothesis is rejected, significant reduction in priapic events will be demonstrated statistically.

Assuming uniformity in the occurrence of priapic events before exposure to crizanlizumab treatment, baseline will be adjusted for 26 weeks for analysis purpose.

Percent reduction from baseline in priapic events will be tested using a nonparametric test (i.e. Wilcoxon's Sign Rank test). Hodges-Lehmann estimate of median percent reduction in priapic events will also be reported, along with corresponding 95% confidence intervals. The significance of the efficacy endpoints will be assessed at  $\alpha = 0.05$  level.

The primary analysis will be performed on all FAS subjects who have completed 26 weeks on treatment.

Number of priapic events will be summarized at baseline (adjusted for 26 weeks) and by Week 26, and percent reduction from adjusted baseline by Week 26 will be summarized by mean, standard deviation (SD), lower quartile (Q1), median, upper quartile (Q3), minimum and maximum. In addition, subgroup analysis of the primary endpoint will also be performed based on the number of priapic events categories (i.e.  $<7$ ,  $7 - 13$ ,  $14 - 21$ ,  $\geq 22$ ) at baseline. The priapic events categories may be re-grouped to ensure that there is adequate number of subjects in each

category for analysis. Additional analyses will also be performed for the subgroups of subjects with acute priapism and subjects who have experienced priapic episodes lasting less than one hour.

Further details will be provided in the SAP.

The imputation of missing data caused by intercurrent events will be handled by defining the estimand framework. The primary estimand is described by the following four attributes:

1. The target population comprises Sickle Cell Disease Patients with Priapism
2. The primary variable is percent reduction from baseline period in priapic events (priapism defined as unwanted, or painful erection lasting at least 60 min self-reported) by 26 weeks.
3. Treatment of interest: investigational drug will be a crizanlizumab solution provided every 4 weeks with an additional loading dose 2 weeks after the first dosing. Further details about the investigational treatment are provided in [Section 6](#).
4. The intercurrent events are the events occurring after enrollment that may impact the treatment effect. The intercurrent events of interest are listed below:
  - a. Treatment discontinuation
  - b. Initiation or discontinuation of HU/HC or L-Glutamine (or other therapies to treat SCD and or to prevent/reduce VOCs such as voxelotor and erythropoietin) or of prophylactic treatment for priapism
  - c. Intake of analgesic (including opioids) or ad hoc transfusions administered temporarily
5. The summary measure is the median percentage change from baseline period in priapic events (priapism defined as unwanted, or painful erection lasting at least 60 min self-reported) by 26 weeks.

### **Handling of the intercurrent events:**

The approach of accounting for intercurrent events is as follows:

- **For the intercurrent events 4a:** Only data before study treatment discontinuation will be included. The data between treatment discontinuation and week 26 will be imputed using Poisson distribution (primary method to handle missing data).
- **For the intercurrent events 4b:** Only data before initiation or discontinuation of HU/HC or L-Glutamine (or other therapies to treat SCD and or to prevent/reduce VOCs such as voxelotor and erythropoietin) or of prophylactic treatment for priapism will be included. The data between initiation or discontinuation of therapies to treat SCD or of prophylactic treatment for priapism and week 26 will be imputed using Poisson distribution (primary method to handle missing data).
- **For the intercurrent events 4c:** Data after intake of analgesic (including opioids) or ad hoc transfusions administered temporarily will be included (treatment policy strategy).

#### **12.4.3 Handling of missing values/censoring/discontinuations**

The missing values will be imputed for the primary analysis. Missing values will be imputed using Poisson distribution, assuming the same effect as observed data. Imputed datasets

(approximately 1,000) will be created, and each dataset will be analyzed using the method described for primary endpoint. The results will be combined using Rubin's rule ([Barnard J and Rubin DB 1999](#)) Further details will be outlined in the SAP.

As stated in [Section 12.4.4](#) , the volume of missing data generated due to COVID-19 crisis will also be assessed and sensitivity analyses will be performed.

#### **12.4.4 Sensitivity and supportive analyses**

##### **Sensitivity analyses**

- To explore the robustness of analysis, sensitivity analysis as a 'tipping point approach will be performed for the primary endpoint to evaluate the impact of a deviation from the MAR assumption. The basic idea is to first impute the missing values using the multiple imputation (MI) method based on the missing at random (MAR) assumption, then adjusted by a delta value. The delta adjusting approach described in [Ratitch et al \(2013\)](#) will be used to find the tipping point, in a spectrum of conservative missing not at random (MNAR) assumptions, at which conclusions change from being favorable to being unfavorable. After such a tipping point is determined, clinical judgment can be applied as to the plausibility of the assumptions underlying this tipping point. A detailed description of the analysis will be provided in SAP.
- As part of the sensitivity analysis, treatment policy strategy (that is, data after the intercurrent events will be included) will also be applied for the intercurrent events 4a and 4b, described in [Section 12.4.2](#).
- As part of the sensitivity analysis, the primary analysis will be analyzed on all subjects in FAS without missing data.
- Additionally, as the study is ongoing during COVID 19 pandemic, the impact of COVID-19 (if any) on the primary endpoint will be assessed in accordance to FDA's guideline entitled "Statistical Considerations for Clinical Trials During the COVID-19 Public Health Emergency". The analysis (as stated below) will be repeated on the FAS excluding the subjects with missing data due to COVID-19.
  - Percent reduction from baseline in priapic events will be tested using a nonparametric test (i.e., Wilcoxon's Sign Rank test). Hodges-Lehmann estimate of median percent reduction in priapic events will also be reported, along with corresponding 95% confidence intervals. The significance of the efficacy endpoints will be assessed at  $\alpha = 0.05$  level.

Further details will be provided in the SAP, as needed.

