### **3 Study design**

This is a multicenter, prospective, phase II, single-arm, open-label study to assess the efficacy and safety of crizanlizumab in SCD patients with priapism.

A total of approximately 36 male subjects aged  $\geq$  12 years, who meet all of the inclusion criteria and none of the exclusion criteria will be eligible for the study. Subjects with  $\geq$  4 priapic events during the 14 week pre-screening period and having at least 3 priapic events during the 12 week screening period with at least 1 event occurring within 4 weeks prior to the first treatment, will be included in the study.

The baseline period is defined as the 12 weeks screening period. Eligible subjects will be treated with crizanlizumab at a dose of 5.0 mg/kg. From the first screening visit until the end of follow-up, the total study duration will be up to 79 weeks (including 12 weeks of screening, 52 weeks of treatment and 15 weeks of follow-up as applicable). The primary analysis of the study will be conducted by 26 weeks to assess efficacy of crizanlizumab in those patient population, who have completed 26 weeks of treatment. The secondary [REDACTED] endpoints will be assessed by 26 weeks and/or 52 weeks. Subjects will be followed for safety for up to 105 days (15 weeks) after the last dosing if applicable. Subjects who will receive commercially approved

crizanlizumab approximately 4 weeks after their last dose of study treatment, do not need to complete the 105-day follow-up. The safety follow-up of these subjects will be at the End of Treatment (EOT) visit. All other subjects are required to complete the 105-day follow-up visit.

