5.4 Statistical models

5.4.1 Analysis supporting primary objective(s)

Primary analysis

Wilcoxon signed rank test

The SAS procedure PROC UNIVARIATE will be used to perform Wilcoxon signed-rank test.

Hodges-Lehmann Estimation

The SAS procedure PROC NPAR1WAY will be used to compute the Hodges-Lehmann estimate.

Handling of missing data

Generating the multiple imputation

The missing values will be imputed for the primary analysis.

- To fill in the missing values (i.e. number of priapic events by 26 weeks), generate Poisson distributed random variables with a rate parameter based on the same effect as observed data. Compute 1000 such complete datasets. Use seed 10105.
- Each datasets will be analyzed using the same method as described in primary analysis.

Analyzing the imputed data

- The resulting estimates and standard errors will be combined using Rubin's rule ([Barnard J and Rubin DB 1999](#)), by the SAS procedure MIANALYZE.

Tipping point analysis for priapic events by 26 weeks

As a sensitivity analysis to evaluate the impact of missing data, a tipping point analysis will be performed for the primary endpoint.

The primary endpoint will be re-analyzed on the delta-adjusted datasets to see if the conclusions change. If not, a larger delta is chosen and the process will be repeated until the conclusion is overturned. The tipping point is the delta value which will cause the primary endpoint to be no longer statistically significant. A series of analyses on a range of delta values (i.e., 1,2,3,.....) will be performed to find the tipping point.

For each delta value, the following steps will be performed.

1. Impute the missing values (i.e. number of priapic events by 26 weeks) by generating Poisson distributed random variables with a rate parameter based on the same effect as observed data. Use seed 10105.
2. After the imputation obtained in above step, make the imputed value worse by a value of delta (i.e., add delta to the imputed value). Note: delta = 0 represents the standard missing at random (MAR).
3. The final imputed delta-adjusted dataset where all missing values are filled, will be analyzed using method as described in the primary analysis.

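### The tipping-point analysis adds the same whole number of events to every imputed count, so one delta means a different departure from missing at random for each subject; the shift should be put on the event rate

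*Protocol*

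**What the plan says.** Protocol 12.4.4 describes a delta-adjusted tipping-point analysis of the primary endpoint, in which missing values are imputed "based on the missing at random (MAR) assumption, then adjusted by a delta value". It leaves the scale of delta to the SAP and says that afterwards "clinical judgment can be applied as to the plausibility of the assumptions underlying this tipping point".

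SAP 5.4.1 supplies the scale. Step 1 is: "Impute the missing values (i.e. number of priapic events by 26 weeks) by generating Poisson distributed random variables", with a rate that reflects the same effect as the observed data. Step 2 is: "make the imputed value worse by a value of delta (i.e., add delta to the imputed value". The grid is in whole events: "A series of analyses on a range of delta values (i.e., 1,2,3,.....) will be performed to find the tipping point". Delta rises until significance is lost. No scaling by missing time, baseline count or subject rate is stated.

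On what is imputed, Protocol 12.4.2 says of stopping treatment: "The data between treatment discontinuation and week 26 will be imputed using Poisson distribution". It treats a start or stop of background SCD therapy or priapism prophylaxis the same way, and SAP 2.5.3 repeats both rules. Other missing values are also imputed (SAP 2.5.4). SAP 2.5.5 runs the tipping-point analysis only if the amount of missing data is significant, without a threshold.

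**The concern.** A tipping point is useful when its delta can be read as one statement about what happened while the subject was unobserved, so that a clinician can call that statement plausible or not. Here the outcome is a count, subjects differ widely in event rate, and missing stretches may differ in length. A fixed number of added events is a severe assumption for a subject with few events and a mild one for a subject with many.

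The endpoint makes the imbalance worse. It is a percent reduction from the subject's own baseline, so an added event moves low-baseline subjects most. A tipping delta of 3 might be dismissed as implausible because of the low-rate subjects, although for high-rate subjects it falls short of losing the treatment effect.

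**Working it through.** **The plan's own figures.** Protocol 12.9 and SAP 3 assume a mean baseline rate of 10.0 by 26 weeks, a 25% reduction, SD of the difference 5.0 and two-sided alpha 0.05. A one-sample t test with difference 10.0 × 0.25 = 2.5, SD 5.0 and n = 34 has 80.8% power. A signed-rank simulation with normal differences gives 79.1%. With 5% dropout, 34/0.95 = 35.8, so 36. The sample size reproduces and is not affected by this point. The plan states no tipping-point value to reproduce.

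**Inputs for the delta check**
- Lowest baseline count b: 3, from the entry rule "having at least 3 priapic events during the 12 week screening period" (Protocol 3).
- High baseline count: 22, the lower edge of the top subgroup category, which SAP 2.2.1 applies to the 12-week baseline as well as to the adjusted one. It is a planned category, not an observed count.
- Baseline scaling: × 26/12 (SAP 2.5.2).
- Reduction r: 25% (planned), with 50% shown as a range.
- Missing weeks w: not in the documents. The values below are illustrative.

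**Formula.** Events that total loss of effect would add in the gap: T = (b/12) × w × r. Then delta/T shows how far a given delta goes relative to total loss.

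| b | w | r | T | delta = 1 | delta = 3 |
|---|---|---|---|---|---|
| 3 | 26 | 25% | 1.63 | 0.62 | 1.85 |
| 22 | 26 | 25% | 11.92 | 0.08 | 0.25 |
| 3 | 4 | 25% | 0.25 | 4.0 | 12.0 |
| 22 | 20 | 25% | 9.17 | 0.11 | 0.33 |
| 3 | 4 | 50% | 0.50 | 2.0 | 6.0 |
| 22 | 20 | 50% | 18.33 | 0.05 | 0.16 |

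**Spread between subjects at the same delta**
- Equal gaps: 22/3 = 7.3-fold, whatever the gap, r or delta. If 22 is taken on the 26-week-adjusted scale instead, against 3 × 26/12 = 6.5, it is 22/6.5 = 3.4-fold.
- Unequal gaps (the 4-week and 20-week rows): (22 × 20)/(3 × 4) = 36.7, about 37-fold. This requires an imputed count that covers only the missing weeks.

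**Grid.** On that same reading, at the planned mean of 10 events per 26 weeks, total loss over w weeks is 2.5w/26 events at a 25% effect. This equals 1 at w = 10.4. At a 50% effect it is 5w/26, which equals 1 at w = 5.2. For shorter gaps the first step already exceeds total loss, and the grid has no point between same effect and no effect.

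**Endpoint scale.** One added event costs 100/6.5 = 15.4 points of percent reduction at b = 3. At b = 22 it costs 100/47.7 = 2.1 points.

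**The same shift on the rate.** If the rate expected under missing at random is multiplied by k, total loss of a 25% effect is k = 1/0.75 = 1.33 for every subject, and 2.0 for a 50% effect. With the additive delta = 1, a 25% effect and gap scaling, the implied k is (0.75 + 1)/0.75 = 2.33 for b = 3, w = 4, and (27.5 + 1)/27.5 = 1.04 for b = 22, w = 20.

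**The case against.** Several objections have force.

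- **Gap length.** SAP 5.4.1 calls the missing value the number of events by 26 weeks. It does not say that the Poisson mean is scaled to missing weeks or is subject-specific. If the whole 26-week count is imputed, delta = 3 on an expected 7.5 is a 1.4-fold increase whatever the gap. Protocol 12.4.2 and SAP 2.5.3 support the gap reading, but the text is ambiguous, so the 37-fold figure and the grid thresholds are conditional. The 7.3-fold spread from baseline alone does not need that reading.
- **Loss of benefit.** A reader might infer that loss of benefit is never tested. The documents do not support that. Sensitivity analysis 2 (SAP 2.5.5) uses data collected after treatment discontinuation or a change of therapy, and the additive ladder rises until the result tips. What is missing is narrower: a defined return to the subject's own baseline rate over time that stays unobserved. Protocol 9.1.1 asks subjects to return for assessments where possible, but its stated minimum after stopping treatment is new or concomitant treatments and adverse events, not priapic events.
- **Size of total loss.** A reader might take 2.5 events as the most an average subject can lose. That holds only for an effect of exactly 25%; at 50% it is 5.
- **Long gaps.** The primary set is subjects who completed 26 weeks on treatment (Protocol 12.4.2, SAP 2.5.2), which removes most long gaps after discontinuation. Gaps after a change of therapy remain, because Protocol 6.2.1.1 does not make such changes a default reason to leave the trial. Missing diary data remain too.
- **Practical weight.** Planned dropout is 5% of 36, about 2 subjects, and a rank test bounds the influence of any one of them.
- **A pure multiplier is not a full cure.** If rates are subject-specific, a subject with no observed events has an imputed mean of zero, and no k moves it. An additive delta does.

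**Conclusion.** The point holds as a limit on interpretation. The additive delta is computable, but it does not express one assumption across subjects, so the tipping value cannot be judged for plausibility as planned. The firm figure is a 7.3-fold difference between 3 and 22 baseline events with equal gaps, taking 22 on the 12-week scale and the same proportional effect in both subjects. The wider spread of about 37-fold assumes a subject-specific mean scaled to missing weeks, and gaps of 4 and 20 weeks chosen for illustration.

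A reader might go further and conclude that the primary result is unprotected or likely to be wrong. The documents do not support that: at the planned dropout the effect on the primary conclusion is likely small, and sensitivity analysis 2 covers part of the ground. Dropout is only a proxy, however, since the plan gives no expected frequency of therapy changes or missing diary data. This is a minor, cheap improvement.

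**What to change.** In SAP 5.4.1:

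1. Add a named scenario in which each subject's unobserved days are imputed at his own screening-period rate. The entry rule keeps that rate above zero, so it also moves subjects with no observed events on treatment.
2. In step 2, replace the added count by a shift on the rate for unobserved days. One form is: imputed rate = MAR rate + f × (own baseline rate − MAR rate), with f = 0, 0.25, 0.5, 1, 1.5 and so on. Here f = 0 is missing at random and f = 1 is full loss of effect. State that the rate is not lowered where the MAR rate already exceeds baseline. A multiplier k is an acceptable alternative if it is reported alongside scenario 1. Report the tipping f or k.
3. State that the Poisson mean is scaled to missing days, and whether it is subject-specific or pooled.

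The cost is SAP wording and slightly more programming in the imputation step. No new data are needed, and the primary test does not change.
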